2.3. Sample size

Calculation of the sample size is based on the following works:

1. Efficacy of probiotics in prevention of acute diarrhea: a meta-analysis of masked, randomized, placebo-controlled trials. Sazawal S, Hiremath G, Dhingra U, Malik P, Deb S, Black RE. *Lancet Infect Dis.* 2006 Jun; 6(6):374-82. Review. PMID: 16728323. DOI:10.1016/S1473-3099(06)70495-9.
3. McFarland LV. Meta-analysis of probiotics for the prevention of antibiotic associated diarrhea and the treatment of *Clostridium difficile* disease. *Am J Gastroenterol.* 2006 Apr;101(4):812-22.
5. H. Szajewska, M. Kolodziej. Systematic review with meta-analysis: *Lactobacillus rhamnosus* GG in the prevention of antibiotic-associated diarrhoea in children and adults. *AP&T*, Volume 42, Issue 10, November 2015, Pages 1149–1157.

The primary endpoint is an assessment of the incidence of AAD from Day 1 to the last day of the course of LRG-002 use vs. placebo in ARD patients receiving standard antimicrobial therapy. The primary efficacy criterion will be considered met if the odds ratio for AAD between the two groups is statistically significantly greater than 1 (i.e., the incidence of AAD in the LRG-002 group is lower than in the placebo group).

A test based on the odds ratio was used to calculate the sample size.

The following data were obtained from Figure 2 in a meta-analysis [1] (only data for AAD were used):

Using only data for AAD studies in adults from the cited publication, the rate for the control group is 0.24 and for the treatment group 0.14.

Using only data for LGG studies in adults and children, the rate for the control group is 0.26 and for the treatment group 0.15.

In meta-analysis [14], figures from Table 1 give a rate of 0.196 for a treatment group and 0.29 for a placebo group (only studies for adults with LGG were taken into consideration).

In meta-analysis [15], figures from Table 2 give a rate of 0.188 for a treatment group and 0.269 for a placebo group (only studies for adults with LGG were taken into consideration).

The consideration of AAD studies for LGG from [16], concerning infections in adults (including *H. pylori*), gives 0.14 for a probiotic group and 0.22 for a control group.

Combining all the strains, we obtain an incidence of 0.26 for the placebo and 0.15 for the probiotic group.

The following indicators were used for calculations:

1. The difference of absolute risks of AAD in the placebo group and the treatment group is expected to be positive.

The incidence of AAD = 0.26 is assumed for the placebo and 0.15 for the treatment group.

Possibility of type I error: 0.05

Power of the study is 80%, which corresponds to the type II error: 0.20.

Statistical hypothesis is the evidence of superior efficacy:

$$H_0: OR = 1$$

$$H_1: OR \neq 1,$$

where OR is the odds ratio between both groups.

The ratio between the treatment and placebo group sizes is 1:1.

Amount of the patient in each group could be calculated using the following formula [2]:

$$n_T = n_R = \left(\frac{Z_{1-\alpha/2} + Z_\beta}{p_T - p_R} \right)^2 [p_T(1-p_T) + p_R(1-p_R)] = 208$$

Thus, the minimum number of patients required for statistical analysis is 416 (208 patients per group). Taking into account a 20% withdrawal rate, one needs to randomize 520 subjects (260 patients per group).

3. General analysis values

3.1. Clinical and statistical significance

All the statistical tests within this study will be performed at 95% confidence level (threshold value p to confirm statistical significance is less than 0.05). The two-sided statistical criteria will be used for all other studied parameters.

3.2. Procedure for missing, unanalyzable, and questionable data

During the monitoring visits to the study sites, the clinical study specialists (monitors) authorized by the Sponsor will analyze CRFs for data completeness. In the absence of data on CRFs and the availability of relevant information in the primary documentation, questions for investigators and regulations to address inconsistencies will be formulated. At the database check, the expert in statistics authorized by the Sponsor, the Data Control and Processing managers will analyze the study results for questionable, missing, and unanalyzable data, which might be the basis for the questions for investigators. If possible, the investigators will eliminate the errors identified in CRFs and inform the Principal Investigator and authorized representatives of the Sponsor hereof. In case the identified data errors cannot be eliminated after the completion of the patients' participation in the study, the analysis of the resulting parameter sensitivity to questionable data will be conducted in the statistical analysis. Information on missing, questionable, and unanalyzable data will be summarized in the final clinical study report. A method of filling in the missing data based on maximum likelihood estimation (MLE) for the primary endpoint will be applied if needed. The analysis of the rest of endpoint types and other parameters will be performed only on the basis of the available information without filling in the missing data in view of the short duration of the clinical study.

4. Study participants

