#### **10.6 Missing, Suspect and Non-Amendable-To-Analysis Data Procedures**

During monitoring visits to the clinical center, Clinical Research Associates (Monitors) authorized by the Sponsor will analyze the CRF of the study subjects for the lack of necessary data. If there is any missing data in CRF and the relevant information is available in the source documentation, relevant queries to investigators shall be spelled out, as well as instructions for elimination of discrepancies. During check of the database, the Statistician, authorized by the Sponsor, and Managers for Data Control and Processing will determine whether there were any uncertain, missed, or non-amendable-to-analysis data, based on which queries to investigators can be defined. The investigators, if possible, eliminate the detected errors in CRF, and inform the Principal Investigator and authorized representatives of the Sponsor thereof. If the detected errors in the data cannot be eliminated after the completion of the patient's participation in the study, sensitivity of the resulting parameters to the presence of suspected data will be analyzed during the statistical analysis of the data. Information on missing, suspected and non-amendable-to-analysis data will be presented in the final clinical study report. For the primary endpoint, the method of filling in the missing values will be applied on the basis of the maximum likelihood estimation (MLE), if necessary [64]. For all other types of endpoints and other parameters, the analysis will be carried

out only using actually available information, without data fulfillment, which is associated with a short duration of the clinical study.

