4.2.2. ITT population receiving treatment

The intention-to-treat (ITT) population: All randomized subjects who received at least one dose of the investigational medicinal product/placebo and have completed at least one visit aimed at the evaluation of efficacy parameters (i.e., at least all the procedures of Visit 1).

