4.2.3. Per protocol set

The per protocol (PP) population: All randomized subjects who completed participation in the study in accordance with the protocol (have completed the prescribed period of treatment and follow-up without significant deviations from the protocol).

5. Demographics and baseline characteristics

All the data obtained in the groups before the study therapy initiation (demographic, laboratory, instrumental, and physical examinations data, vital signs, etc.) will be compared to determine the groups' comparability for analysis.

For quantitative characteristics, it is planned to calculate the following statistics:

- 1) Quantity
- 2) Number of missing values
- 3) Median
- 4) 95% CI for the mean
- 5) Standard deviation
- 6) Median
- 7) Minimum
- 8) Maximum
- 9) First quartile
- 10) Third quartile
- 11) Interquartile range

For categorical variables, it is planned to calculate the following characteristics:

- 1) Absolute number by the group
- 2) Percentage relative to groups

3) Percentage of visits by group

Quantitative variables will be checked for compliance with the normal distribution using the Shapiro–Wilk test.

To compare quantitative data distributed according to the normal distribution, it is planned to use parametric criteria: Student's t-test for dependent/independent samples, analysis of variance (ANOVA) for repeated measurements to compare more than two stages.

To compare quantitative data distributed according to a principle other than normal distribution, it is planned to use standard nonparametric tests: Mann–Whitney U test, Wilcoxon T test for dependent samples, and Friedman test for dependent samples.

Comparison of the frequencies of indicators between treatment groups will be carried out using Pearson's chi-square test if the number of points in each cell of the crosstab is ≥ 5 , or Fisher's exact test if at least one of the crosstab cells contains < 5 points.

In the event that any of the initial data reveal the incomparability of the study groups (statistically significant differences in demographic and other initial data between the groups), an analysis of the parameters of efficacy and safety will be additionally carried out together with the primary planned analysis using multivariate statistics (ANCOVA or logistic regression depending on the type of parameter under study), adjusted for the initial indicator(s), according to which the groups initially differed.

6. Concomitant therapy

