7.1. Primary endpoint analysis

Assessment of the incidence of AAD from Day 1 to the last day of the course of LRG-002 use vs. placebo in ARD patients receiving standard antimicrobial therapy. The primary efficacy criterion will be considered met if the odds ratio for AAD between the two groups is statistically significantly greater than 1 (i.e., the incidence of AAD in the LRG-002 group is lower than in the placebo group).

STATISTICAL ANALYSIS PLAN

The primary efficacy endpoint will be analyzed using a fixed-factor logistic regression model for the treatment group and age group. The treatment effect will be displayed using the adjusted odds ratio and the corresponding two-sided 95% confidence interval.

PCT will be calculated using the following set of functions of the R language:

- `glm` – building a logistic regression model;
- `summary` – displays the regression coefficients with an indication of the statistical significance;
- `confint` – displays confidence intervals for regression coefficients.

An example of a planned way of using these functions is shown in Figure 2. In the figure, the *Outcome* variable encodes the outcome (AAD – yes/no), *Treatment* encodes belonging to a particular study group, the *Age* variable encodes the age category (over or under 50 years old). The *p*-value is highlighted in red, the two-sided confidence interval is highlighted in blue, according to which the decision on reaching the PCT will be made.

```
> model_out <- glm(Outcome ~ Treatment + Age, data = df, family = "binomial")
> summary (model_out)
Call:
glm(formula = Outcome ~ Treatment + Age, family = "binomial", data = df)
Deviance Residuals:
    Min       1Q   Median       3Q      Max
-0.3327 -0.3327 -0.1635 -0.1635  2.9402

Coefficients:
            Estimate Std. Error z value Pr(>|z|)
(Intercept)  -4.3090    0.5949  -7.243 4.4e-13***
Treatment2    1.4427    0.6520   2.213 0.0269*
Ageage >=50  -0.5368    0.6558  -0.819 0.4130
```

```
Signif. codes: 0 '****' 0.001 '**' 0.01 '*' 0.05 '.' 0.1 ' ' 1

(Dispersion parameter for binomial family taken to be 1)

Null deviance: 135.35 on 509 degrees of freedom Residual deviance: 128.52 on
507 degrees of freedom
AIC: 134.52

Number of Fisher Scoring iterations: 7

> confint(model_out)
Waiting for profiling to be done...
      2.5%      97.5%
(Intercept) -5.7259968 -3.3150721
Treatment2  0.2808742  2.9311963
Age >=50    -2.0306660  0.6338301
```

Figure 2. Running functions for calculating PCT

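### Missing AAD outcomes are to be filled in by an unspecified likelihood-based method with no pooling step; filling once is worse than analysing the observed outcomes, by an amount that depends on how it is done

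*SAP*

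**What the plan says.** SAP 3.2: "A method of filling in the missing data based on maximum likelihood estimation (MLE) for the primary endpoint will be applied if needed". All other endpoints are analysed "only on the basis of the available information without filling in the missing data".

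Protocol 10.6 has the parallel sentence, "the method of filling in the missing values will be applied on the basis of the maximum likelihood estimation (MLE), if necessary [64" (closing bracket follows). Item 64 in protocol section 16 is a randomised trial of Lactobacillus GG in children with functional abdominal pain.

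Neither document states the fill model, its covariates, whether values are predicted or drawn, how many fills are made, how the extra uncertainty is carried, or what makes filling necessary.

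SAP 7.1 fits one logistic regression on treatment and age group. It says "the two-sided confidence interval is highlighted in blue, according to which the decision on reaching the PCT will be made", and the p-value is marked in the same output. The code is introduced with "An example of a planned way of using these functions is shown in Figure 2". No other route to the decision is described.

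A patient enters the ITT set on at least one dose if they "have completed at least one visit aimed at the evaluation of efficacy parameters (i.e., at least all the procedures of Visit 1"). Per-protocol patients must "have completed the prescribed period of treatment and follow-up without significant deviations from the protocol". Neither protocol 10.1.2 nor SAP 7.1 says which set is primary. The protocol synopsis attaches the 208 per arm to the per-protocol population.

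SAP 3.2 and protocol 10.6 provide a sensitivity analysis for data errors that cannot be resolved. Protocol 10.1.2 allows further ones. None is named for missing outcomes.

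**The concern.** A value inserted by a model carries no new information about its patient. If it then enters the regression as an observed outcome, the software counts it as information and the standard error is too small, unless the model that produced it ignored treatment. In that case the filled values are alike in both arms and dilute the treatment effect.

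There is a harmless meaning of maximum likelihood here: maximise the likelihood of the observed data. With only the outcome missing, this is the same as fitting the SAP 7.1 model to patients with an outcome. It does not fit the text. SAP 3.2 sets the primary endpoint apart from the other endpoints precisely because those are not filled in, and under the harmless meaning that contrast would be empty.

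What is at stake is the trial's single confirmatory test. The same sentence can be carried out in several ways that give different p-values, and the choice could be made after the data are seen.

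**Working it through.** **Inputs.** AAD 0.26 on placebo and 0.15 on LRG-002, two-sided 0.05, 80% power, 1:1, 20% withdrawal, 260 per arm randomised (SAP 2.3; sidedness from protocol 10.4). Null rate 0.205 = (0.26 + 0.15)/2. *Assumed:* the missing share *m*, random and equal by arm unless stated, and the age-stratum split.

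**The plan's own figure.** ((1.960 + 0.8416)/0.11)² × (0.15 × 0.85 + 0.26 × 0.74) = 207.5, so 208. Then 208/0.80 = 260. Both reproduce.

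**Single fill, treatment in the model.** Let R be the true variance of the treatment effect divided by the variance the regression reports. Type I error is 2 × (1 − Φ(1.96/√R)).
- Fitted-probability fill: the estimate rests on n(1 − m) patients per arm but is reported as if on n, so R = 1/(1 − m).
- One random draw: the draws add noise of relative size m, so R = 1/(1 − m) + m.

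| *m* | Fitted probability | Random draw |
|---|---|---|
| 1% | 5.12% | 5.23% |
| 2% | 5.23% | 5.47% |
| 5% | 5.61% | 6.20% |
| 10% | 6.30% | 7.49% |
| 20% | 7.96% | 10.36% |

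Simulating the SAP 7.1 model at AAD 0.205 (260 per arm, strata 50/50, 200,000 trials) agrees: 5.7% and 6.2% at 5% missing, 6.3% and 7.4% at 10%. Observed outcomes only: 4.9–5.0%. With 40% aged 50 or over (100,000 trials), null rates of 0.15 and 0.26 give 5.3–6.0% at 5% missing and 6.1–7.3% at 10%.

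**Fill without treatment (age group only).** Type I error at 10% missing is 3.8% (fitted probability), and 4.9–5.0% for a random draw at any *m* examined. The cost is attenuation: the expected risk difference shrinks by the factor 1 − m, here 0.9 × 0.11 = 0.099.

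**Most-likely-class fill.** With AAD below 50%, every missing outcome becomes no AAD. At 10% missing the rates become 0.234 and 0.135, and the odds ratio moves from (0.26/0.74)/(0.15/0.85) = 1.99 to (0.234/0.766)/(0.135/0.865) = 1.96. Type I error is 4.9–5.0% with equal missingness. It reaches 9.1% at an assumed 5% v 15% missing, a split with no basis in the documents.

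**Power at 0.26 v 0.15** (100,000 trials; 87.9% with nothing missing):

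| Handling | 10% missing | 20% missing |
|---|---|---|
| Observed outcomes | 84.2% | 79.7% |
| Fill without treatment, fitted | 81.5% | 72.5% |
| Fill without treatment, draw | 80.1% | 70.2% |
| Most-likely class | 83.2% | 77.6% |
| Fill with treatment, fitted / draw | 86.5% / 85.6% | 85.2% / 83.5% |

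The last row's apparent gain comes from the understated standard error.

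**Lower event rates.** The SAP 7.1 example output shows "Null deviance: 135.35 on 509 degrees of freedom". That matches 15 events in 510: −2 × [15 ln(15/510) + 495 ln(495/510)] = 135.35, a rate of 2.9%. At a 3% rate the Wald test is conservative (3.3–3.4% on observed outcomes at 5–10% missing). A single fill with treatment then gives 4.0–4.2% at 5% missing and 4.7–5.4% at 10%.

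**The case against.** Four points on the other side have weight.

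1. *The inflation belongs to one reading.* It needs each outcome filled once, from a model containing treatment, and then analysed as observed. No section says all three. This stands: the figures are conditional. But each literal way of filling once has its own defect (understated error, attenuation, or coding every leaver as no AAD), and none improves on the observed outcomes.

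2. *The code is only an example.* That is so, and an illustration on one data set does not show that filled data would go unpooled. The gap remains because pooling is mentioned nowhere else.

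3. *Few outcomes may be missing.* Leavers are seen or telephoned (protocol 6.3.1.1) and gaps are queried against source. Study drug stops on exclusion (protocol 6.3.2) while the endpoint runs to the last day of dosing (protocol 10.1.2), so a leaver's observation window could be read as closing at exit. Filling applies only if needed. At 1–2% missing the excess is at most about 0.5 percentage points. This stands.

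4. *The trial is sized on the per-protocol set*, where few outcomes would be missing. This also stands, although neither document names that set as primary.

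It is also fair to say that multiple imputation by arm and stratum adds almost nothing to the observed-outcome model when only the outcome is missing. The fix below therefore does not require it.

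**Conclusion.** The fill-in sentence should be replaced. As worded it points to inserting values, and the only described analysis would treat them as observed. The size depends on assumptions the documents do not settle. With treatment in the fill model and AAD at 15–26%, type I error is 5.1–5.5%, 5.6–6.2% and 6.3–7.5% at an assumed 1–2%, 5% and 10% missing; at a 3% event rate it is about nominal or below at 5–10% missing. Without treatment in the fill model, error is controlled and power at 10% missing drops by roughly 3 to 4 points. The most-likely-class fill does little harm when missingness is equal by arm. All of this concerns the ITT set.

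A reader might infer three stronger things that the documents do not support:
- *That the plan as written inflates type I error.* It does so only under one of several readings.
- *That 20% of outcomes will be missing, giving 8.0–10.4%.* The 20% is a withdrawal ceiling, not a missing-outcome rate.
- *That the example output shows the expected AAD rate.* It is illustrative code and says nothing about the true rate.

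This is a change the sponsor should make. It is not evidence that the trial's conclusion would be wrong.

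**What to change.** In SAP 3.2 and protocol 10.6, replace the fill-in sentence with:

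1. AAD recorded before exit counts as AAD.
2. The SAP 7.1 model is fitted to observed outcomes. No singly filled values enter it.
3. If imputation is used for the ITT set, it is multiple imputation including arm, age stratum and exit day, combined by Rubin's rules.
4. One sensitivity analysis departing from missing at random is reported: missing counted as AAD in both arms, or a tipping point.
5. Reference [64] in protocol 10.6 is corrected or removed.

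Exit day belongs in item 3 because item 1 keeps leavers who already had AAD while other leavers become missing, which matters when exits differ by arm. With onset and exit days assumed uniform over 14 days (20,000 trials), 5% v 15% leaving gives type I error of 6.0% for observed outcomes, 6.1% for imputation by arm and stratum, and 5.2% once exit day is added. With equal exits of 5–20%, imputation by arm and stratum gives 4.9–5.2%. Power and low event rates were not examined for the imputation scheme.

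The cost is a slightly wider confidence interval than a single fill would give, wording in two sections, and modest programming.

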4.1. Patient distribution

It will be a double-blind, randomized study.

Patients will be included by applying stratified randomization in two strata:

Age < 50 years

Age ≥ 50 years

Each treatment group will be balanced as 1:1 in each stratum.

Stratified randomization is a two-stage procedure in which patients who enter a clinical study are first grouped into strata. Within each stratum, patients are then assigned to treatment according to separate randomization schedules. The randomization module of EDC system assigns patient unique randomization code based on a treatment group and stratum. Randomization schedules will be hidden from medical personnel and all other persons involved in the study (monitors, data management, biometry, sponsor, etc.), except for the specialists responsible for IMP labeling and emergency unblinding.

4.2. Study population

4.2.1. Safety population

The safety population (safety): All randomized subjects who received at least one dose of the investigational/reference product and have completed at least one visit aimed at the evaluation of safety parameters (i.e., at least Visit 1). As distinct from ITT population, the safety population will be analyzed depending on actually received treatment (not only prescribed) (in case of difference between the prescribed and received therapies).

4.2.2. ITT population receiving treatment

The intention-to-treat (ITT) population: All randomized subjects who received at least one dose of the investigational medicinal product/placebo and have completed at least one visit aimed at the evaluation of efficacy parameters (i.e., at least all the procedures of Visit 1).

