**Visit 1 (Day 1)**

Patients start participating in the study after signing the Informed Consent Form. Procedures at Visit 1 for patients in each study group:

- Collection of demographic data (year of birth, sex, age);
- Body weight and height measurements;
- Medical history;
- Reporting concomitant treatment (including medications, medical devices and food supplements);
- Complaints reporting;
- Physical examination;
- Vital signs assessment (heart rate [HR], blood pressure [BP]), body temperature [BT], respiratory rate [RR]);
- Complete blood count;
- Blood chemistry profile;
- COVID-19 Antibody (IgM / IgG) combined express-test;
- Urine pregnancy test;
- A 12-lead electrocardiogram;
- Evaluation of the inclusion/non-inclusion criteria;
- Randomization;
- Dispensing of the investigational medicinal product (IMP) / placebo;
- Dispensing of patient diary, mercury thermometer and respective training;
- Dispensing of laboratory kit with the necessary supplies to collect stool samples;
- Adverse event assessment.

Having completed the screening tests, eligible patients will be randomized on the same day to receive either LRG-002 or matching placebo capsules, each as an adjunct to the prescribed antibiotic (see inclusion criteria). The treatment group will be determined by randomization at a 1:1 ratio. Study subjects will be supplied with the

patient diary and blinded investigational product (investigational medicinal product or placebo) depending on the assigned treatment group. Patients will be able to start study treatment only after receiving appropriate training. On Day 1, the study will be started in both groups from randomization and administration of the first dose of the investigational product depending on the assigned group after randomization:

**Group T, treatment with LRG-002:** a single dose of 1 oral hard capsule taken during meals with some water; the product is to be taken orally 2 times per day for 14 days.

**Group R, treatment with placebo:** a single dose of 1 oral hard capsule taken during meals with some water; the product is to be taken orally 2 times per day for 14 days.

If the appointment is received in the afternoon, the administration of one capsule is allowed on the first day. The interval between taking the oral antibiotic and IMP/Placebo should be at least 3 hours in both groups.

IMP/Placebo capsules must not be taken concomitantly with alcohol, fruit juices or hot beverages.

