### **7.2 Compliance control**

Compliance will be controlled by review of patient's diary and counting the amount of the medicinal product remaining.

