### **10.8 Selection of subjects for analysis**

For the analysis, the following data sets will be used:

- Population of all included patients (intention-to-treat, ITT): all randomized subjects who administered at least one dose of the investigational medicinal product / placebo and completed at least one visit to evaluate the efficacy parameters (i.e. at least all procedures of visit 1).
- Population of patients who completed the study according to the Protocol (per protocol, PP): all randomized subjects who completed participation in the study according to the Protocol (completed the prescribed period of treatment and follow-up without significant deviations from the Protocol).
- Safety population: all randomized subjects who administered at least one dose of the investigational medicinal product / reference medicinal product and completed at least one visit to evaluate safety parameters (i.e. at least Visit 1). Unlike the ITT population, the safety population will be analyzed according to the actual treatment received rather than the prescribed treatment (if the differences are identified between the treatment prescribed and actually received).

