2.2.3. Study stages

It is allowed to conduct visits in the form of outpatient visits by a doctor and a nurse at the patient's home.

Screening/randomization/therapy initiation (Visit 1)

Visit 1 is scheduled for Day 1. At this visit, the doctor evaluates the patient's eligibility for the study. If non-inclusion criteria are not identified, randomization is carried out, the patient is given the investigational/reference product, a laboratory kit for collecting stool samples with appropriate instructions, a patient diary, and training on filling out the patient diary (Appendix 3).

Procedures at Visit 1:

Visit 1 (Day 1)

- Collection of demographic data (year of birth, sex, age);
- Measurement of weight and height;
- Anamnesis collection;
- Registration of concomitant therapy (including other medications, dietary supplements, and the use of medical devices);
- Collection of complaints, actualization of anamnesis;
- Physical examination;
- Assessment of vital signs (heart rate, respiration rate, blood pressure, temperature);
- Hematology;
- Biochemistry;
- Express test for the qualitative detection of immunoglobulin G (IgG) and immunoglobulin M (IgM) antibodies to COVID-19;
- Urine pregnancy test;
- 12-lead ECG;
- Evaluation of inclusion/non-inclusion criteria;
- Randomization;
- Dispensing of an investigational medicinal product (IMP)/ placebo;
- Issuance of a patient diary, mercury thermometer, and appropriate instructions;
- Issuance of a laboratory kit with the necessary consumables for collecting stool samples;

- Evaluation of adverse events.

Visit 2 (Day 7 ± 2)

Procedures performed at Visit 2 in each treatment group:

- Collection of complaints, actualization of anamnesis;
- Records on the concomitant therapy;
- Weight measurement;
- Physical examination;
- Measurement of vital signs;
- Hematology;
- Biochemistry;
- Adverse events registration;
- Evaluation of exclusion criteria;
- Issuance of a laboratory kit with the necessary consumables for collecting stool samples (if necessary);
- Compliance evaluation (diary completion, administration of the investigational medicinal products);
- Assessment of diarrhea based on patient diary entries and face-to-face interviews in relation to antibiotic use (AAD or non-AAD) according to the investigator's opinion (in the absence of stool analysis results at the time of the visit, the assessment is carried out after the investigator receives the results from the laboratory).

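### The ITT set is conditioned on completing every Visit 1 procedure, so a dosed patient with an observed AAD outcome can be dropped for one missed baseline item

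*SAP*

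**What the plan says.** SAP 4.2.2 builds the ITT set from two conditions. The first is dosing: "All randomized subjects who received at least one dose of the investigational medicinal product/placebo". The second is a visit condition: they must "have completed at least one visit aimed at the evaluation of efficacy parameters (i.e., at least all the procedures of Visit 1"). Protocol 10.8 repeats the second almost word for word: "completed at least one visit to evaluate the efficacy parameters (i.e. at least all procedures of visit 1").

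The safety set in SAP 4.2.1 is looser on the visit. Its patients must "have completed at least one visit aimed at the evaluation of safety parameters (i.e., at least Visit 1"), with no mention of all procedures. The per-protocol set in SAP 4.2.3 starts from all randomised subjects and asks for the treatment and follow-up period without significant deviations. It does not require ITT membership.

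SAP 2.2.3 lists 18 Visit 1 items. They include height and weight, hematology, biochemistry, a COVID-19 antibody test, a urine pregnancy test, an ECG, randomisation, product dispensing and, for example, "Issuance of a patient diary, mercury thermometer, and appropriate instructions". Classification of diarrhea as AAD or not first appears at Visit 2.

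On order, the synopsis states: "Having completed the screening tests, eligible patients will be randomized on the same day". It then states: "On Day 1, the study will be started in both groups from randomization and administration of the first dose of the investigational product".

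**The concern.** The condition is presented as a minimum of efficacy evaluation, but the visit it names yields no information on the primary endpoint. Completeness of baseline work-up is therefore used to decide whether an observed primary outcome counts. Three consequences follow.

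- A patient with a full diary and a settled AAD classification can be removed for a gap unrelated to diarrhea. Such gaps are plausible, because both documents allow visits at the patient's home while still requiring bloods and an ECG.
- The sets do not nest. If the missed item is not judged a significant deviation, the patient can be in per-protocol and safety but not in ITT. Comparing ITT with per-protocol results then loses its usual meaning.
- The word *all* needs interpretation. The SAP list includes a urine pregnancy test without qualification, whereas protocol 5.2.3 limits it to women of reproductive potential. Neither document says how inapplicable or missed items are to be judged, so membership rests on a decision that could be made after data are seen.

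At stake is the retention of known primary outcomes and an accurate label for the set.

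**Working it through.** **Inputs.** AAD 0.26 on placebo and 0.15 on LRG-002, two-sided alpha 0.05, power 80%, 1:1 allocation, 20% withdrawal, 520 randomised (SAP 2.3). The share of patients who would miss a Visit 1 item is not in the documents, so it is varied below.

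**Reproducing the plan's figure.** The SAP formula uses the unpooled variance 0.26×0.74 + 0.15×0.85 = 0.3199.

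- n per arm = (1.960 + 0.842)² × 0.3199 / 0.11² = 7.849 × 0.3199 / 0.0121 = 207.5, rounded up to 208.
- 208 / 0.80 = 260 per arm, 520 in total.

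The sample size reproduces, and this point does not affect it.

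**Cost of exclusions.** Power = Φ(0.11 / √(0.3199/n) − 1.96), with the design rates unchanged:

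| Assumed loss from ITT | n per arm | Power |
|---|---|---|
| 0% | 260 | Φ(3.136 − 1.96) = 88.0% |
| 1.9% | 255 | 87.4% |
| 5% | 247 | Φ(3.057 − 1.96) = 86.4% |
| 10% | 234 | 84.5% |
| 20% | 208 | 80.1% |

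Each 1% lost is about 5 of 520 patients; 5% is 26 patients, 13 per arm. With a pooled variance the 0% and 5% rows read 87.7% and 86.0%.

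**How few exclusions can matter.** These counts are assumed and chosen to be borderline; the test is an unadjusted Wald test on the log odds ratio.

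- 68/260 placebo versus 50/260 LRG-002 gives p = 0.060. Removing one LRG-002 patient with AAD (49/259) gives p = 0.049.
- 68/260 versus 49/260 gives p = 0.047. Removing one placebo patient with AAD (67/259) gives p = 0.056.

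The effect can go either way. This shows why known outcomes should not be lost to a clerical rule; it is not evidence of bias.

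**Can the exclusion depend on arm?** The synopsis places the screening tests before randomisation, so a missing ECG, blood test or COVID-19 test cannot be caused by the assigned arm. Dispensing, diary and kit issue and the adverse event check follow randomisation, but take place at the same visit with identical blinded packs (protocol 5.4.2).

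**The case against.** The best case for leaving the text alone is that the loss will be tiny. Most of the listed items are needed to confirm eligibility, so a randomised patient will normally have them. Blinding makes any gap unrelated to arm, and even a 5% loss leaves power above the planned 80%. All of that stands, and it sets the size of the point. It gives no reason to keep the condition, which protects nothing.

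Visit 1 is also not empty of efficacy data: weight there is the baseline for the weight-change endpoint. That stands too, but a missing weight affects that endpoint only and is no ground for discarding an AAD outcome.

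The one-dose requirement is a familiar modified-ITT choice. The heading of SAP 4.2.2 discloses it, and in a blinded trial never starting treatment is unlikely to depend on arm. Keeping it is defensible if the set is named accordingly.

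A reader might infer something stronger: that patients who never return a diary fall out of ITT because dosing cannot be shown, so that membership depends on diarrhea and biases the comparison. Protocol 7.2 invites this, since "Compliance will be controlled by review of patient's diary and counting the amount of the medicinal product remaining". The documents do not support it. Neither definition mentions diary return, and the diary is collected at Visit 3. Protocol section 13 requires administration dates in the source records. Protocol 6.3.1.1 has early leavers seen or telephoned, with available information recorded. A patient who completed Visit 1, took a dose and then disappeared stays in ITT with a missing outcome under SAP 3.2. Any bias from such outcomes arises because they were never observed. Likelihood estimation under missing-at-random, with only treatment and age in the model, would draw on the same observed outcomes, so redefining the set would not remove it.

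**Conclusion.** The point holds as a defect of definition with a small expected effect. Both documents condition ITT on completing all Visit 1 procedures, none of which assesses AAD. Applied literally, this removes observed primary outcomes and lets per-protocol patients fall outside ITT. The expected cost is precision: about 88.0% to 86.4% power at an assumed 5% loss. Material bias between arms is not expected.

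The power figures rest on the design rates, on an assumed loss, and on this set being used for the primary analysis. The last is not stated: SAP 7.1 names no analysis set, and the synopsis ties the 208 per arm to the per-protocol population. That is a separate gap. What remains open on dosing is narrow: neither document says how to classify a patient whose intake is undocumented.

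**What to change.** In SAP 4.2.2 and protocol 10.8:

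- Delete the Visit 1 procedures condition and define ITT as all randomised patients, analysed in the arm assigned.
- If the sponsor prefers to keep the one-dose condition, call the set modified ITT and add a rule: a patient to whom product was dispensed counts as dosed unless records, or a full pack returned unused, show otherwise.
- State that a patient without a diary stays in the set with AAD status missing, handled under SAP 3.2.

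The cost is a few sentences and no new data. Protocol 11.2 classes changes that can affect statistical methods as substantial, so editing protocol 10.8 may need that route. Protocol 10.7 also allows a departure to be listed and justified in a SAP finalised before the final analysis, and described in the study report. The scientific downside is small: a few patients with incomplete baseline data, or possibly undosed, enter the set and may slightly dilute the effect.
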